6.1.2. Adverse Events**6.1.2.1. Main Analysis**

- Estimand: The percentage of participants reporting AEs from study intervention administration through 1 month after administration ([Section 2.2](#)).
- Analysis set: Safety population ([Section 4](#)).
- Analysis time point: From the study intervention administration through 1 month after administration.
- Analysis methodology: Descriptive statistics ([Section 5.2.1](#)).
- Reporting results: AEs will be categorized according to MedDRA terms. Descriptive summary statistics (counts, percentages, and associated Clopper-Pearson 95% CIs) will be provided for any AEs, by each SOC and each PT within the SOC for each group.

6.1.2.2. Supplementary Analyses

Related AEs, severe AEs, and immediate AEs (within the first 30 minutes after administration) will also be summarized for each group. Any AEs reported after informed consent signing and prior to the study intervention administration will not be included in the analyses but will be listed.

6.1.3. Serious Adverse Events

6.1.3.1. Main Analysis

- Estimand: The percentage of participants reporting SAEs from administration through 1 month after administration (Section 2.2).
- Analysis set: Safety population (Section 4).
- Analysis time point: From administration through 1 month after administration.
- Analysis methodology: Descriptive statistics (Section 5.2.1).
- Reporting results: SAEs will be categorized according to MedDRA terms. Counts, percentages, and the associated Clopper-Pearson 95% CIs of SAEs will be provided for each group.

6.2. Secondary Endpoint

6.2.1. [REDACTED] OPA Titers 1 Month After Administration

6.2.1.1. Main Analysis

- Estimand: [REDACTED] OPA GMT 1 month after administration (Section 2.2).
- Analysis set: Evaluable immunogenicity population and mITT population (as appropriate) (Section 4).
- Analysis time point: 1 Month after administration.
- Analysis methodology: GMT and the 2-sided 95% CI from each group will be derived based on the t distribution (Section 5.2.2.1).
- Reporting results: The GMT and 95% CI for [REDACTED] OPA will be provided for each group.

PFIZER CONFIDENTIAL

Term	Percentage
GMOs	75%
Organic	85%
Natural	82%
Artificial	55%
Organic	88%
Natural	80%
Artificial	60%
Organic	92%
Natural	88%
Artificial	50%
Organic	80%
Natural	78%
Artificial	45%

6.4. Baseline and Other Summaries and Analyses

6.4.1. Baseline Summaries

6.4.1.1. Demographic Characteristics

Demographic characteristics, including age, sex, race, and ethnicity, will be summarized for the safety population for each group and overall.

6.4.1.2. Medical History

Each reported medical history term will be mapped to an SOC and PT according to MedDRA. The number and percentage of participants having at least 1 diagnosis, overall, and at each SOC and PT level, will be summarized by group for the overall safety population.

6.4.2. Study Conduct and Participant Disposition

6.4.2.1. Participant Disposition

The number and percentage of randomized participants will be included in the participant disposition summary. In addition, the numbers and percentages of participants who received the study administration, who completed the follow-up visits, and who withdrew from the study, along with the reasons for withdrawal, will be tabulated by group (according to randomized group assignment). The reasons for withdrawal will be those specified in the database.

PFIZER CONFIDENTIAL

Participants excluded from each analysis population will also be summarized separately, along with the reasons for exclusion, by group.

6.4.3. Study Administration Exposure

6.4.3.1. Administration Timing and Administration

The number and percentage of participants randomized and receiving the study intervention will be tabulated for each group and overall, for all randomized participants. The denominator for the calculation of percentages is the total number of randomized participants in the given group or overall.

6.4.4. Concomitant Vaccinations and Concomitant Medications

Each concomitant vaccine will be summarized according to the ATC fourth-level classification. The number and percentage of participants receiving each concomitant vaccine after the study intervention will be tabulated by group. The safety population will be used. Concomitant medications will be summarized in a similar way as concomitant vaccines.

6.5. Safety Summaries and Analyses

AE and SAE summaries and analyses are described in the Primary Endpoints section ([Section 6.1.2](#) and [Section 6.1.3](#)).

7. INTERIM ANALYSES

No interim analysis is planned in this study.

7.1. Introduction

Not applicable.

7.2. Analysis Timings

Statistical analyses will be carried out as specified below:

- An analysis will be conducted when safety data through approximately 1 month after study intervention administration are available.
- Immunogenicity data of OPA and IgG results through Visit 2 (1 month after study intervention administration) may be analyzed, when available, for 1 or more immunogenicity endpoints [REDACTED]
[REDACTED]
- Final analysis of safety and immunogenicity will be conducted when complete OPA and IgG results become available after the completion of the study. [REDACTED]
[REDACTED]

This is an open-label Phase 1 exploratory study. Immunogenicity data reviews by the sponsor may be conducted at any time the data are available to aid in decision-making for the sponsor programs.

Certain analyses may be combined if the data become available around the same time. Additional analyses may be conducted or combined if required for regulatory purposes or for further clinical evaluation of the study intervention.

9. APPENDICES

Appendix 1. List of Abbreviations

Abbreviation	Term
13vPnC	13-valent pneumococcal conjugate vaccine
20vPnC	20-valent pneumococcal conjugate vaccine
AE	adverse event
ATC	Anatomic Therapeutic Chemical (classification system)
BLQ	below the limit of quantitation
BMI	body mass index
[REDACTED]	[REDACTED]
CI	confidence interval
CRF	case report form
CRM ₁₉₇	cross-reactive material 197 (nontoxic variant of diphtheria toxin)
e-diary	electronic diary
ELISpot	enzyme-linked immunosorbent spot
GM	geometric mean
GMC	geometric mean concentration
GMFR	geometric mean fold rise
GMT	geometric mean titer
ICD	informed consent document
IgG	immunoglobulin G
IRT	interactive response technology
LLOQ	lower limit of quantitation
LOD	limit of detection
MedDRA	Medical Dictionary for Regulatory Activities
[REDACTED]	[REDACTED]
[REDACTED]	[REDACTED]

Abbreviation	Term
[REDACTED]	[REDACTED]
[REDACTED]	[REDACTED]
N/A	not applicable
OPA	opsonophagocytic activity
[REDACTED]	[REDACTED]
PCV15	15-valent pneumococcal conjugate vaccine
PT	preferred term
RAC	reductive amination chemistry
[REDACTED]	[REDACTED]
SAE	serious adverse event
SAP	statistical analysis plan
[REDACTED]	[REDACTED]
SOC	system organ class
US	United States
WHO	World Health Organization

Appendix 2. Reactogenicity Data Consolidation

For reactogenicity collected in the e-diary, redness and swelling will be measured and recorded in measuring device (caliper) units, and then categorized during analysis as mild, moderate, or severe based on the grading scale in Table 5. Measuring device units can be converted to centimeters according to the following scale: 1 measuring device unit = 0.5 cm. Pain at the injection site will be assessed by the participant as mild, moderate, or severe according to the grading scale in Table 5. The systemic events of fatigue (tiredness), headache, muscle pain, and joint pain will be assessed by participants as mild, moderate, or severe according to the grading scale in Table 6. Grade 4 reactions and events, which can only be classified by an investigator, will be collected as an AE on the CRF. For reactogenicity collected in the AE CRF, the grading scales will be based on the AE intensity scale in Table 7. If a local reaction or systemic event is captured in more than 1 data source, eg, e-diary, unplanned assessments, and/or AE CRF, the highest grade will be used in the safety summary analysis.

Table 5. Grading Scales for Local Reactions Collected From the E-Diary

Local Reaction	Mild Grade 1	Moderate Grade 2	Severe Grade 3 ^a	Grade 4 ^b
Redness	5 to 10 measuring device units = >2.0 to 5.0 cm	11 to 20 measuring device units = >5.0 to 10.0 cm	>20 measuring device units = >10.0 cm	Necrosis or exfoliative dermatitis
Swelling	5 to 10 measuring device units = >2.0 to 5.0 cm	11 to 20 measuring device units = >5.0 to 10.0 cm	>20 measuring device units = >10.0 cm	Necrosis
Pain at injection site	Does not interfere with activity	Interferes with activity	Prevents daily activity ^c	Emergency room visit or hospitalization for severe injection site pain

Abbreviation: CRF = case report form.

Note: If the size of the redness and/or swelling falls between 2 measuring device units, the higher measuring device unit number will be recorded in the e-diary.

- Participants experiencing Grade 3 local reactions are required to contact the investigator site. In the event that the participant does not call, the investigator will call the participant.
- Grade 4 assessment should be made by the investigator; Grade 4 local reactions will not be collected in the e-diary but will be collected as AEs on the CRF. The intensity of the local reaction should be graded using the AE intensity grading scale.
- Prevents daily activity, eg, results in missed days of school or work or is otherwise incapacitating.

Table 6. Grading Scales for Systemic Events Collected From the E-Diary

	Mild Grade 1	Moderate Grade 2	Severe Grade 3^a	Grade 4^b
Fatigue (tiredness)	Does not interfere with activity	Some interference with activity	Prevents daily routine activity	Emergency room visit or hospitalization for severe fatigue
Headache	Does not interfere with activity	Some interference with activity	Prevents daily routine activity	Emergency room visit or hospitalization for severe headache
Muscle pain	Does not interfere with activity	Some interference with activity	Prevents daily routine activity	Emergency room visit or hospitalization for severe muscle pain
Joint pain	Does not interfere with activity	Some interference with activity	Prevents daily routine activity	Emergency room visit or hospitalization for severe joint pain

Abbreviation: CRF = case report form.

- a. Prevents daily routine activity, eg, results in missed days of school or work or is otherwise incapacitating; includes use of narcotics for analgesia.
- b. Grade 4 assessment should be made by the investigator; Grade 4 systemic events will not be collected in the e-diary but will be collected as AEs on the CRF. The intensity of the systemic event should be graded using the AE intensity grading scale.

Table 7. Assessment of AE Intensity Grade

Grade	If required on the AE page of the CRF, the investigator will use the adjectives MILD, MODERATE, and SEVERE to describe the maximum intensity of the AE. For purposes of consistency, these intensity grades are defined as follows:	
1	MILD	Does not interfere with participant's usual function.
2	MODERATE	Interferes to some extent with participant's usual function.
3	SEVERE	Interferes significantly with participant's usual function.

Document Approval Record

Document Name: C4801001 Statistical Analysis Plan V2 Clean Copy, 05Dec2022

Document Title: A PHASE 1, RANDOMIZED, OPEN-LABEL TRIAL TO EVALUATE THE SAFETY AND IMMUNOGENICITY OF PNEUMOCOCCAL CONJUGATE FORMULATIONS IN HEALTHY ADULTS 18 THROUGH 49 YEARS OF AGE

Signed By:	Date(GMT)	Signing Capacity
-------------------	------------------	-------------------------

PPD

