8.3.2.1. Local Reactions

From Day 1 through Day 7 following study intervention administration at Visit 1, where Day 1 is the day of study intervention administration, participants will be asked to assess redness, swelling, and pain at the injection site and to record the symptoms in the e-diary in the evening. Redness and swelling will be measured and recorded in measuring device (caliper) units (range: 1 to 21+) and then categorized during analysis as mild, moderate, or severe based on the grading scale in [Table 2](#). Measuring device units can be converted to centimeters according to the following scale: 1 measuring device unit = 0.5 cm. Pain at the study intervention injection site will be assessed by the participant as mild, moderate, or severe according to the grading scale in [Table 2](#). The participant will be prompted to contact the investigator if he/she experiences a severe (Grade 3 or above) local reaction to assess the reaction and perform an unscheduled assessment or visit as appropriate. Only an investigator is able to classify a participant's local reaction as Grade 4, after physical examination of the participant or documentation from another medically qualified source (eg, emergency room

or hospital record). If a participant experiences a Grade 4 local reaction, the investigator must immediately notify the sponsor. Site staff will educate the participants regarding signs and symptoms that would prompt site contact. Grade 4 reactions will be collected as AEs on the CRF. The event will be graded using the AE intensity grading scale (Section 10.3.3).

The procedure for notification of the sponsor is provided in the investigator site file or equivalent.

Table 2. Grading Scales for Local Reactions

	Mild Grade 1	Moderate Grade 2	Severe Grade 3^a	Grade 4^b
Redness	5 to 10 measuring device units = >2.0 to 5.0 cm	11 to 20 measuring device units = >5.0 to 10.0 cm	>20 measuring device units = >10.0 cm	Necrosis or exfoliative dermatitis
Swelling	5 to 10 measuring device units = >2.0 to 5.0 cm	11 to 20 measuring device units = >5.0 to 10.0 cm	>20 measuring device units = >10.0 cm	Necrosis
Pain at injection site	Does not interfere with activity	Interferes with activity	Prevents daily activity ^c	Emergency room visit or hospitalization for severe injection site pain

Note: If the size of the redness and/or swelling falls between 2 measuring device units, the higher measuring device unit number will be recorded in the e-diary.

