3.1.2.1. Local Reactions and Systemic Events

The local reactions, including redness, swelling, and pain at the injection site, and the systemic events, including fever, fatigue (tiredness), headache, muscle pain, and joint pain, are reported in the e-diary from Day 1 through Day 7 after administration, where Day 1 is the day of administration. The e-diary entries from the participant will be the primary data source for these events. However, any events related to administration that are considered local reactions or systemic events starting within 7 days after administration, that happen to be entered on the AE CRF, will be consolidated with e-diary data, and included in the reactogenicity summary. This section describes derivations with details for the assessment of the reactogenicity data: severity level, duration, and onset day.

Severity and Maximum Severity

The definitions for reactogenicity severity collected from the e-diary and from AEs are described in [Appendix 2](#).

For each local reaction or systemic event after administration, the maximum severity grade will be derived for the collection period (Day 1 through Day 7, where Day 1 is the day of administration) as follows:

maximum severity grade = highest grade (maximum severity) within 7 days after administration (Day 1 through Day 7) among severity grades reported for that local reaction or systemic event

Temperatures recorded in degrees Fahrenheit will be programmatically converted to degrees Celsius first for reporting. Fever will be grouped into ranges for the analysis according to Table 4. Maximum temperature range over the period from Day 1 through Day 7 will be mapped into the ranges described in Table 4 for summary of maximum temperature. For fever reported on the AE CRF within 7 days after administration, mild fever will be grouped in the $\geq 38.0^{\circ}\text{C}$ to 38.4°C range, moderate fever will be grouped in the $>38.4^{\circ}\text{C}$ to 38.9°C range, and severe fever will be grouped in the $>38.9^{\circ}\text{C}$ to 40.0°C range (unless specifically noted to be $>40.0^{\circ}\text{C}$ in an unplanned visit contact or noted on the AE CRF).

Table 4. Ranges for Fever

$\geq 38.0^{\circ}\text{C}$ to 38.4°C
$>38.4^{\circ}\text{C}$ to 38.9°C
$>38.9^{\circ}\text{C}$ to $40.0^{\circ}\text{C}^{\text{a}}$
$>40.0^{\circ}\text{C}^{\text{a}}$

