6. ANALYSES AND SUMMARIES

6.1. Primary Endpoints

6.1.1. Local Reactions and Systemic Events

6.1.1.1. Main Analysis

- Estimands:
 - The percentage of participants reporting local reactions (redness, swelling, and pain at the injection site) within 7 days after administration ([Section 2.2](#)).
 - The percentage of participants reporting systemic events (fever, headache, fatigue, muscle pain, and joint pain) within 7 days after administration ([Section 2.2](#)).
- Analysis set: Safety population ([Section 4](#)).
- Analysis time point: Within 7 days after administration.
- Analysis methodology: For percentages of each group, the 2-sided Clopper-Pearson CIs will be calculated ([Section 5.2.1](#)).
- Reporting results: Count and percentage of participants with the indicated endpoint and the associated 2-sided 95% CI for each and any local reaction or systemic event after administration in each group will be provided by maximum severity across severity levels.

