**Figures:**

Bar charts with the proportions of participants for each local reaction or systemic event on each day (Day 1 through Day 7) and any day (Day 1 through Day 7) will be plotted for each group, with different patterns displayed in the bar charts for different severity levels (each day) and different maximum severity levels (any day), respectively.

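### By the AE-CRF route the SAP names, a Grade 4 prompted reaction is displayed as Severe at most, and whether a 4 can appear depends on the source

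*SAP*

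**What the plan says.** SAP Appendix 2 gives Grade 4 its own column for redness, swelling and injection-site pain (Table 5) and for fatigue, headache, muscle pain and joint pain (Table 6). Only an investigator may assign it. Footnote b of Table 6 says that "Grade 4 systemic events will not be collected in the e-diary but will be collected as AEs on the CRF", and Table 5 has the same footnote for local reactions.

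The scale for that source is then fixed: "For reactogenicity collected in the AE CRF, the grading scales will be based on the AE intensity scale in Table 7". In Table 7 "the investigator will use the adjectives MILD, MODERATE, and SEVERE to describe the maximum intensity of the AE", numbered 1 to 3. The protocol agrees. Section 8.3.2.1 says "Grade 4 reactions will be collected as AEs on the CRF. The event will be graded using the AE intensity grading scale", Section 8.3.2.2 has the equivalent rule for systemic events, and the scale in Section 10.3.3 also ends at 3.

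When an event is held in more than one source, "eg, e-diary, unplanned assessments, and/or AE CRF, the highest grade will be used in the safety summary analysis".

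The output is split by severity. Under SAP 6.1.1.1, counts, percentages and CIs "will be provided by maximum severity across severity levels". The accompanying figures have "different patterns displayed in the bar charts for different severity levels (each day) and different maximum severity levels (any day), respectively".

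Fever is treated separately. SAP 3.1.2.1 maps a mild, moderate or severe AE-CRF fever to a temperature range, and keeps the range above 40.0°C when that is specifically noted "in an unplanned visit contact or noted on the AE CRF".

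**The concern.** The plan defines a top category, reserves it for the investigator and requires immediate notice to the sponsor when it occurs. The source to which it assigns that category is then graded on a scale without it. Nothing visible says that Grade 4 is meant to be merged into Severe for display.

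Table 7 also measures something different. It grades interference with usual function, whereas Grade 4 redness or swelling is defined by tissue damage, and Grade 4 pain or systemic events by emergency care or hospital admission. A skin necrosis that interferes little with function could be recorded below Severe.

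Reactogenicity is a primary endpoint, reported by maximum severity, for candidates not previously given in clinical studies (protocol 2.3). A reader of those tables could not tell a Grade 4 event that came in through the AE CRF from an ordinary Severe one. Two similar events could also be displayed differently because different sources captured them.

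**Working it through.** **Inputs.** Grade definitions and routing: SAP Appendix 2, Tables 5 to 7. Combination rules: SAP 3.1.2.1 and Appendix 2. Unscheduled-visit procedures: protocol 8.10.3. Group size 45: protocol 9.5. The plan states no figure on this point. As a check on n, protocol Table 5 at a 5% true rate gives 1 − 0.95^45 = 90.06%, which matches the printed 90.1%.

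**Step 1: the highest grade each source can supply.**

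| Prompted term | E-diary | AE CRF (Table 7) | Unscheduled visit (protocol 8.10.3) | Highest displayed |
|---|---|---|---|---|
| Redness, swelling (2) | 1–3, from size | 1–3 | Diameters measured; other findings go to the AE page | 3 |
| Pain, fatigue, headache, muscle pain, joint pain (5) | 1–3 | 1–3 | Graded by protocol Tables 2 and 3, which include a 4 | 3, or 4 if an unplanned assessment recorded a 4 |
| Fever (1) | Temperature | Mapped to ranges; above 40.0°C kept if noted | Temperature | Above 40.0°C |

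The terms add up: 2 + 5 + 1 = 8.

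**Step 2: apply the highest-grade rule.** Over the e-diary and the AE CRF, max(3, 3) = 3. A displayed 4 needs a third source that holds a 4. For redness and swelling none is described. For the other five terms the unscheduled visit could hold one. So, possibly, could the telephone contact recorded in the CRF or the assessment of ongoing reactions at the next visit.

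**Step 3: is that third source assured?** No. Protocol 8.3.2.1 and 8.3.2.2 let the investigator classify Grade 4 from an emergency room or hospital record, and for systemic events also by telephone. Protocol 8.10.3 lists reasons why the site visit may not take place.

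**Step 4: size, for one assumed Grade 4 event in a group of 45.** Clopper-Pearson limits (SAP 5.2.1):

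- Grade 4 row if the classification is carried through: 1/45 = 2.2%. Lower limit 1 − 0.975^(1/45) = 0.06%. The upper limit solves (1 − p)^45 + 45p(1 − p)^44 = 0.025, giving p = 11.77%.
- Grade 4 row, if shown, by the AE-CRF route: 0/45 = 0%. Upper limit 1 − 0.025^(1/45) = 7.87%. The participant is counted as Severe or lower.
- Any severity: 1/45 in both cases.

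The documents give no Grade 4 rate, so this says nothing about how often it would happen.

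**The case against.** The strongest reply is that this is deliberate. Both documents state the same rule, the tables can be computed as written, and no sentence commits the SAP to a Grade 4 row. The agreement is real, so this is not a contradiction between documents. But agreement on how to record AE intensity is not a decision to merge Grade 4 into Severe in the reactogenicity tables, and neither document states one.

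Second, protocol 8.10.3 is headed in part for a suspected Grade 4 reaction, has pain and systemic events graded on scales that contain a 4, and ends in a CRF assessment page. The highest-grade rule would then deliver the 4. This stands for five terms. A reader might infer that no Grade 4 can ever reach the tables for any of the seven; the documents do not support that.

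Third, the fever rule is an imperfect precedent. Fever is reported in temperature ranges, so AE-CRF adjectives need a mapping, and temperatures above 40.0°C can also come from the e-diary. The rule shows that a top category can be kept, not that a parallel rule was overlooked.

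Fourth, the harm is limited. All analyses are descriptive. Grade 4 events reach the AE tables, hospital admissions are SAEs, and the sponsor is told at once. This holds, and it lowers the importance of the point, but it does not correct the severity display.

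**Conclusion.** The point holds as a small correction to the SAP. By the AE-CRF route, a Grade 4 event in any of seven prompted terms is displayed as Severe at most. For redness and swelling no visible route gives a 4. For the other five terms the display may depend on which source captured the event. One event in 45 would move 2.2 percentage points out of a Grade 4 row and into Severe or a lower row.

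Two further inferences are tempting and not supported. One is that such an event would always read as Severe: Table 7 grades function, so it may read lower. The other is that Grade 4 events disappear from safety reporting: only the severity split of the reactogenicity output is affected.

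The conclusion rests on the visible text. Redacted text follows Table 4 in SAP 3.1.2.1, the section that derives severity, duration and onset, and the CRF is not among the documents. Either could already hold the classification, so confidence is moderate.

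**What to change.** Change the SAP only:

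- In Appendix 2, state that a prompted reaction or event which the investigator classifies as meeting a Table 5 or Table 6 Grade 4 definition is analysed as Grade 4 in the reactogenicity severity tables and figures, whatever its Table 7 intensity.
- Name the data source for that classification: an existing CRF field if there is one, otherwise a flag on the AE or unplanned-assessment page.
- Include a Grade 4 category in the SAP 6.1.1.1 tables and the bar charts.
- Keep Table 7 intensity for the AE tables.

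Because AE intensity is still recorded on Table 7, the protocol text and the grading-table footnotes can stand. The cost is a short SAP edit and possibly one CRF field. The investigator already makes the classification, so no participants, visits or procedures are added. If redacted text or an existing field already covers this, a cross-reference in Appendix 2 is enough.
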